## 8.1 Missing data

We will make every effort to minimize missing data. Trial enrollment, completeness of data collection, and fidelity of follow-up procedures will be reviewed and reported during study team meetings which will be conducted on a monthly basis. As the majority of data collected is part of the standards of care that are routinely collected in the patients EMR and captured directly from the source, the expected missing data will likely be minimal. The study statistician will conduct frequency reports to assess for missing data, and the study team will trouble shoot any problems encountered. We will report rates of missing data for each outcome by study arm, and known reasons for missing data. For data elements that are used to adjust study comparisons we will use multiple imputation to account for any that are missing at random (MAR).

## 8.2 Sample Size

Difference in ease of use between our standard fetal Doppler and HeraBEAT™ device, as measured by the System Usability Survey (SUS) will be the primary outcome. Approximately 1500 – 2000 expectant mothers receive prenatal care in the obstetric department annually. We aim to recruit 50 participants (50 per arm, with cross-over) for a 99.7% power to detect a 10-point difference in SUS, as this accounts for a withdraw / post-randomization exclusion, estimated as high as 10% (assuming a proportion of expectant mothers to withdraw participation after being enrolled or found to not meet criteria after the fact).

#### 9.0 Potential Limitations

#### 9.1 Conflict of Interest

Obstetric Study Personnel, [name] and [name] [name] are participating Mayo Clinic Innovators, with Know-How license agreement, and stock/equity in HeraMED Ltd. They will not be involved in the direct recruitment of patients for this study. They will participate in future manuscripts of research findings.

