## 5.5 Study Design

As part of current standard of care, pregnant women are initially evaluated by an obstetric physician, nurse practitioner or midwife during the first trimester. During this visit, the study nurse will complete the assessment for eligibility criteria for low risk pregnant women. Upon confirmation of eligibility, the nurse will contact the study coordinator. The study coordinator will approach the patients with study information, ascertain interest in participation, and obtain signed informed consent from those interested.

Between 18 and 20 weeks gestation, all patients complete a fetal sonography assessment for fetal anatomy as part of routine prenatal care. An obstetric provider will review the results with the patient, and confirm that fetal anatomy is normal. Patients with abnormal fetal cardiac or cranial anomalies will be excluded from the study. If the patient interest remains, the study coordinator will confirm ongoing consent and randomize the patient into the study. This will be documented in the appropriate section of the patient's electronic medical records.

Study personnel (obstetric nurses or clinicians) will then provide patients with a study kit, containing the HeraBEATTM device or a standard fetal Doppler device (based on randomization assignment), discuss the limitations of both devices, and instruct patients on the range of normal fetal heart rate.

Study personnel will then observe the study subjects' independent self-administration of the devices in the prenatal clinic after patients receive a brief tutorial of the devices operation. Study subjects will be able to refer to the device instructions for use but will not receive assistance or prompts during this testing session. Study personnel will note any mistakes or difficulties by the subjects on the HeraBEATTM Independent Device Use Assessment Form (Appendix C). Once the observation period is completed, study personnel will document all observations, review and correct any errors made by patients during use of the device, assist patients in confirming accurate use, perform teach back, and provide the study subject with a device for home use. Patients will be instructed to call clinic or Triage with any questions or concerns regarding results of fetal monitoring at home. All calls and recommendations provided will be documented.

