## 5.6 Schema

Patients will be instructed to monitor their fetus once weekly, using their assigned device, from 20 weeks to 36/37 weeks gestation. Patients using the HeraBEATTM device will have their FHR and MHR data displayed on their App, and uploaded to a HIPPA compliant cloud based server, which can be accessed by the healthcare provider for review (*Appendix B*). Patients using the standard handheld Doppler device will be given a study brochure for recording their weekly data. Patients using the HeraBEATTM device will be instructed to bring their device during their outpatient clinical appointments, for comparison of MHR and FHR during their routine clinic appointments using methods documented in *Appendix E*.

After approximately 8 weeks of monitoring, patients will complete a System Usability Survey (SUS Survey), *Appendix D* to assess ease of use of the device, then crossover to the alternate study product.

Patients who are randomized to HeraBEATTM from 20weeks gestation to 28 weeks gestation will be given the standard fetal Doppler. Patients who are randomized to the standard Fetal Doppler will switch to the HeraBEAT.TM At the conclusion of each patient device use (28 weeks and 36 weeks gestation), participants will complete the System Usability Survey (Appendix D) to assess ease of use of each device.

- 1- Nurse assesses eligibility criteria, ascertains mother's interest, and study coordinator will obtain consent and complete randomization Patients will be given home monitoring equipment after their fetal anatomy sonography is complete, inclusion/exclusion criteria confirmed and Patient Usability Form completed (Appendix C).
- 2- After 8 weeks of use, participants will complete the System Usability Scale (SUS) survey (Appendix D), return the first study device and crossover to the second device. An independent device use assessment (Appendix C) will be assessed by study nursing staff and completed for the second device.
- 3- At the conclusion of 8 weeks of self-monitoring with assigned device, participants will complete the System Usability Scale (SUS) survey to assess ease of use (Appendix D).

Prior to registering study participants, all eligibility criteria will have been met and fully documented. Mothers will be randomized by the study coordinator after completion of standard informed consent for participation in clinical research including permission to use Protected Health information.

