## **5.7 Intervention**

All randomized participants will be assigned to an obstetric physician, midwife or combination of physician/nurse practitioner care team that will supervise care during her pregnancy. All laboratory tests, imaging, and standardized evaluations that ensure the safety of the participant and her fetus will be conducted in both arms of the study as per departmental protocol.

Participants will be instructed to seek care (per routine obstetric precautions) for any concerns regarding fetal wellbeing, irrespective of their FHR on home monitoring devices. No clinical decisions will be solely based on the results of home monitoring data. Data uploaded from the HeraBEATTM device will be monitored by trained study personnel via the HeraBEAT dashboard : https://hera-med.rmdy.health/CoachConsole/Account/Login. FHR abnormalities will be investigated, using standard obstetric clinical protocols.

All adverse events (AEs) experienced by the subjects while at home or in the clinic will be recorded on the HeraBEATTM study case report form and evaluated for type of event, severity, whether the AE qualifies as a serious adverse event (SAE), and relationship of the AE to the HeraBEATTM device use.

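### Section 9.1 keeps personnel with equity in the device maker out of recruitment only, leaving tutorials, first-device observer scoring and adverse event causality open to them

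*Combined protocol and SAP*

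**What the plan says.** Section 9.1 describes certain obstetric study personnel as innovators "with Know-How license agreement, and stock/equity in HeraMED Ltd", the HeraBEAT manufacturer. It then states one restriction, "They will not be involved in the direct recruitment of patients for this study", and one continuing role, "They will participate in future manuscripts of research findings".

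Section 5.5 describes the first-device session: "Study personnel (obstetric nurses or clinicians) will then provide patients with a study kit". A brief tutorial precedes the observed session; the person giving it is not named. During unaided use, "Study personnel will note any mistakes or difficulties by the subjects on the" Appendix C form. The same personnel then correct errors and carry out teach-back. Section 5.1 makes this observation the measure for primary objective 1a.

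Section 5.6 is narrower for the second period: "An independent device use assessment (Appendix C) will be assessed by study nursing staff and completed for the second device".

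Section 5.7 requires each adverse event to be evaluated for type, severity, "whether the AE qualifies as a serious adverse event (SAE), and relationship of the AE to the" HeraBEAT device, without saying who does so. Section 8.0 leaves nurses and obstetric providers unblinded and blinds the statistician and data analysts.

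**The concern.** The disclosed interest is in one of the two devices being compared. The restriction covers recruitment, which sections 5.5 and 5.6 already give mainly to the study nurse (eligibility) and the study coordinator (approach, consent, randomisation). It therefore protects a step that the interest-holders would largely not perform. It is silent on tasks where an unblinded person's judgement enters the data directly: what counts as a mistake or difficulty during observed use, and whether an adverse event is related to HeraBEAT. It is also silent on the tutorial and teach-back, which can shape how well a woman performs with a device.

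At stake is the credibility of objective 1a and of the device-relatedness ratings. Blinding the analysts does not help here, because any leaning would already be in the form or the rating when it reached them.

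**Working it through.** The point is about allocation of tasks, and the plan gives no figure to reproduce. The check sets the restriction in 9.1 against each task that involves judgement or training.

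| Task | Who does it, as written | Interest-holders excluded? |
|---|---|---|
| Eligibility, approach, consent, randomisation (5.5, 5.6) | Study nurse and study coordinator | Yes, from direct recruitment (9.1) |
| Tutorial before observed use (5.5) | Not named; same session as the kit hand-over by study personnel | No |
| Appendix C, first device (5.1, 5.5) | Study personnel | No |
| Error correction and teach-back (5.5) | Study personnel | No |
| Appendix C, second device (5.6) | Study nursing staff | Not expressly; the interest-holders' professions are not stated |
| Adverse event severity and relationship (5.7) | Not named | No |
| Investigation of safety concerns (9.2) | Study personnel | No |
| SUS (5.8, 9.4) | Self-reported; e-mail surveys run by the statistical team | Not scored by clinicians |

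The overlap is in the protocol's own terms. Section 9.1 places the interest-holders among obstetric study personnel, and 5.5 gives the observation to study personnel, glossed at the kit hand-over as obstetric nurses or clinicians.

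**Number of exposed assessments.** Inputs: 50 participants, each using both devices (8.2); second-device Appendix C done by nursing staff (5.6).

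- All Appendix C assessments, if everyone completes both periods: 50 × 2 = 100.
- Second-device assessments, assigned to nursing staff: 50.
- First-device assessments, open to any study personnel: 100 − 50 = 50.
- By device, assuming equal allocation (no ratio is stated): 50 ÷ 2 = 25 HeraBEAT and 25 Doppler.

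This is an upper figure. It would be reached only if interest-holders scored every first-device session, and nothing in the documents says that they score any.

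**The case against.** The strongest reply is that this argues from silence. No section assigns the interest-holders to tutorials, Appendix C or adverse event rating; the one role that 9.1 gives them is future manuscripts. Title, signature and consent pages were removed before review, so a separate conflict-management arrangement cannot be excluded. This stands, and it limits the point to what the text permits.

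Several safeguards also stand:

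- The SUS, which 8.2 calls the primary outcome, is self-reported and analysed by blinded staff. Any effect on it would run through the tutorial.
- Objective 1b includes success in finding the fetal heart rate, time to find it and frequency of use from HeraBEAT data, which 3.4 says are sent automatically. That gives an observer-independent check on home use of that device.
- Section 9.2 provides an existing obstetric safety review board, although its independence from the interest-holders and any part in causality ratings are not described. The adverse event gap is an unnamed assessor, not a task left to the interest-holders.

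A reader might infer more than this, in three ways. One is that all 100 Appendix C assessments are exposed; 5.6 gives half of them to nursing staff. Another is that the interest-holders could decide which heart rates count as abnormal in the analysis; 8.0 fixes that numerically, at below 110 or above 160 bpm. The third is that a favourable functionality or safety result could not be told apart from assessor bias. The documents do not support that: Appendix C is not available to show how subjective its items are, finding the heart rate unaided is a fairly concrete event, and the 1b data are a partial check.

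The reply does not close the gap itself. The sponsor judged the interest worth disclosing and restricting, and the restriction misses the tasks that most depend on judgement.

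**Conclusion.** The concern holds as a gap in what 9.1 restricts, not as evidence that biased assessment will occur. As written, personnel with a financial interest in the manufacturer may train women, score first-device Appendix C forms and rate adverse event causality. The exposure is mainly:

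- first-device scoring behind objective 1a: at most about 25 HeraBEAT and 25 Doppler sessions, assuming 50 participants and equal allocation;
- the tutorials and teach-back;
- adverse event severity and relationship, where no assessor is named.

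The size of any resulting bias cannot be estimated from the documents. The conclusion assumes that no conflict-management plan sits on the removed pages; if one exists, 9.1 should refer to it and state its limits. The change is worth making because it is cheap and puts the restriction where it matters, but it does not put the powered SUS comparison in doubt.

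**What to change.** 1. **Section 9.1:** add that personnel with a financial interest in the manufacturer will not give device tutorials or teach-back, complete Appendix C for either device, or judge the severity of adverse events or their relationship to the device.
2. **Section 5.5:** align it with 5.6, so that study nursing staff without such an interest make both Appendix C assessments.
3. **Section 5.7:** state that an existing clinician without such an interest rates adverse events.

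The cost is protocol wording and task allocation. Nursing staff already make the second-device assessment, so the change extends an existing role to the first device. Adverse event rating needs an existing clinician to be designated; the documents do not show that nursing staff could take it on. The downside is slightly less scheduling flexibility.

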#### 9.2 Early Termination / Data Safety Monitoring Board

This study will be monitored for early termination due to any validated safety concerns. The existing obstetric safety review board will be utilized. All reported patient safety concerns will be promptly communicated and investigated by study personnel.

## 9.3 Confidentiality

*Protection of subject privacy:* The privacy of all study participants will be protected by avoiding the use of names on all research data (field notes, transcribed conference call, meetings, etc).

All research material will be maintained on a secure server at Mayo Clinic and locked in file cabinets, and all material will be destroyed seven years following completion of the study. The following entities will be allowed to access their study data:

- The Study Sponsor
- The Study Monitor
- Representatives of the US Food and Drug Administration

Subjects must give permission for the above access in order to participate in the study.

#### 9.4 Data Management

All study coordinators will be required to use the current version of all documents and forms and adhere to the study schedule. Any paper forms collected will be stored within the Obstetrics Department for 3 years under lock. Survey data will be captured via email from study participants using the REDCap system, which is a HIPAA compliant secure data entry system that allows for validated data entry, edit checks and logs of all data changes. Participants unable or unwilling to use the e-mail surveys will be provided a paper copy. The statistical team will develop the REDCap data capture system for the data collection as well as survey collection. The data can be accessed by the statistical team at any time and downloaded into a statistical software package. The survey's via e-mail will be administered and tracked for completion by the statistical team. The statistical team will coordinate with the study coordinator for the mailing and receipt of surveys where mothers have indicated mailing only. The study coordinator will be responsible for the actual mailing of the survey, where the statistical team will provide information to help them coordinate. In cases where a response is not received

within 10 working days a second survey will be mailed or e-mailed, according to mothers' wishes.

Data generated by the HeraBEAT™ device will not contain any patient identifiers. The HeraBEAT™ device generates a UUID- Unique Identifier for each install. The UUID is available in the app at: Home Screen>Settings>About. The app attaches the UUID to saved measurements, which are in turn uploaded to HeraMED's cloud anonymously. No protected health information (PHI) will be stored in HeraBEAT server (the FHR measurement will contain no identifiable data and only the UUID). The HeraBEAT server is HIPAA compliant. The physical storage is in a secured, HIPAA compliant Azure server (Microsoft Azure Cloud Data Center - US East 2 - [name]). The deidentified data can be accessed only by HeraMED CTO and project manager and RMDY CTO, IT manager and DBA. The DB is encrypted using SQL Server Enterprise TDE. The server system keeps a full audit trail.

The Mayo Clinic research team will have secured access to the measurement data via a webbased dedicated service (HeraBEAT Dashboard):

https://hera-med.rmdy.health/CoachConsole/Account/Login

All data, documents, and analysis findings will be password protected and backed up on a routine basis. The data will be stored within the secure system for seven years following completion of the study.

